### **1.1 Rationale**

Results of the primary endpoint from the Phase 3, multicenter, adequate, and well-controlled trial on pain secondary to OA of the knee showed that patients treated with 32 mg FX006 had a rapid, durable, and meaningful analgesic response that was statistically significantly better than placebo treated patients ( $p < 0.0001$ ). This finding was supported by a second, smaller Phase 2b study, where a highly similar pattern of response to 32 mg FX006 was demonstrated. Thus, one aspect of the current clinical development program focuses on evaluating the potential therapeutic effects of FX006 on pain in patients with OA of the shoulder where conventional steroid IA injection shows short-lived efficacy in shoulder OA patients, consistent with the efficacy observed in knee OA. Likewise, FX006 is anticipated to have efficacy in the relief of pain due to OA in the synovial shoulder joint as it shares similar pathogenesis to knee OA.

Shoulder adhesive capsulitis (AC) is a common painful and disabling disorder. The exact etiology is unknown, though the incidence is higher among patients with diabetes than observed in the general population. The disease pathogenesis is characterized by early synovial inflammation, hyperplasia, and hypervascularity, as well as fibroblastic proliferation and fibrosis in the late phase. Patients present with severe pain, limited ranges of motion (ROM), and frozen shoulder. Some patients end up with spontaneous recovery within 2 to 3 years, but up to 40% of patients may experience persistent symptoms with 7% to 15% having some degree of permanent functional loss. Intra-articular corticosteroid injection shows short-lived pain relief with a prolonged effect on passive ROM. It is hypothesized that an extended-release formulation of corticosteroid would provide long-lasting pain relief and functional improvement for patients with shoulder AC.

The glenohumeral joint is a large synovial joint. The injection volume of FX006 (5 mL) is believed to be appropriate as such a volume has been routinely used in the combination of conventional corticosteroid with lidocaine.

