#### **4.2 Exclusion Criteria**

A patient who meets any of the following criteria will be excluded from participation in the study:

1. Is unable to washout from excluded (see Section 5.6.1) or restricted medications (see Section 5.6.2).
2. Has both glenohumeral OA and shoulder AC.
3. Has bilateral AC.
4. Has bilateral glenohumeral OA with glenohumeral OA pain of the shoulder contralateral to the index shoulder  $>3.0$  (0 to 10 NRS) within 1 month prior to the Screening Visit (patient self-report acceptable).
5. Has a history of symptomatic arthritis in other joints of the index shoulder (e.g., acromioclavicular joint or scapulothoracic joint), as confirmed by medical history and physical examination.
6. Has a history or suspicion of full thickness rotator cuff tear in the index shoulder as assessed by the Investigator per medical history and physical examination, ultrasound, or magnetic resonance imaging (MRI) obtained within 6 months of the Screening Visit.
7. Has symptomatic partial rotator cuff tear, tendinopathy, tendonitis, or bursitis in the index shoulder as assessed by Investigator per medical history and physical examination, ultrasound, or MRI obtained within 6 months of the Screening Visit.
8. Has a subchondral bone insufficiency fracture or humeral head necrosis/collapse in the index shoulder based on X-ray used for study qualification.
9. Shoulder AC patients only: Has a history of shoulder surgery in the index shoulder or radiotherapy (e.g., for breast, neck, or upper limb tumors).
10. Glenohumeral OA patients only: Has a previous shoulder injury in the index shoulder with functional limitation  $\geq 1$  month (e.g., dislocation or fracture) or surgery in the index shoulder (including clavicle or scapula) within 52 weeks prior to the Screening Visit.

11. Has an index shoulder with major dysplasia or congenital abnormality, osteochondritis dissecans, acromegaly, ochronosis, hemochromatosis, Wilson's disease, primary osteochondromatosis, or a history of avascular necrosis with secondary OA.
12. Has current or history of infection (e.g., osteomyelitis) in the index shoulder or current skin infection at injection site.

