28. Has known hypersensitivity to TA or PLGA.

29. Has laboratory evidence of infection with human immunodeficiency virus (HIV), a positive test for hepatitis B surface antigen (HBsAg), or positive serology for hepatitis C virus (HCV) with positive test for HCV ribonucleic acid.
30. Has an electrocardiogram (ECG) abnormality judged clinically significant by the Investigator.
31. Has a medical history suggesting the patient will or is likely to require a course of systemic corticosteroids during the study.
32. Has uncontrolled diabetes as indicated by a hemoglobin A1c of >8% (>59 mmol/mol).
33. Has a history or evidence of active or latent systemic fungal or mycobacterial infection (including tuberculosis), or of ocular herpes simplex.
34. Has a history of sarcoidosis or amyloidosis.
35. Has a history of or active Cushing's syndrome.
36. Has used chemotherapeutic agents, immunomodulators, or immunosuppressants other than corticosteroids within 5 years of the Screening Visit.  
  
Note: Restrictions pertinent to corticosteroid use specified in Exclusion Criteria 18, 20, 21, and 22.
37. Has current or history of malignancy within 5 years prior to the Screening Visit, except for basal or squamous cell carcinoma of the skin or cervical carcinoma in situ that has been treated successfully.
38. Has active substance use disorder (drugs or alcohol) or history of substance use disorder within 12 months prior to the Screening Visit as per The Diagnostic and Statistical Manual of Mental Disorders, Fifth Edition.
39. Has received a live (e.g., measles, mumps, and rubella vaccine; chicken pox vaccine; or rotavirus vaccine) or live-attenuated vaccine (e.g., FluMist® or Zostavax®) within 3 months of the Screening Visit.
40. Has used any other investigational drug, biologic, or device within 3 months of the Screening Visit.
41. Has any infection requiring IV antibiotics 4 weeks prior to Day 1 or oral antibiotics 2 weeks prior to Day 1.
42. Has any other clinically significant acute or chronic medical condition(s) that, in the judgment of the Investigator, would preclude the use of an IA corticosteroid or that could compromise patient safety, limit the patient's ability to complete the study, and/or compromise the objectives of the study.
43. Has a contraindication to the use of acetaminophen (allowed rescue pain medicine) per National Product Labeling and the Investigator's judgment.

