### **6.3 Screening Visit (Days -21 to -1)**

The study will include a Screening Period of a maximum of 21 days. The following procedures will be performed at the Screening Visit:

- Obtain informed consent.
- Confirm eligibility based on Inclusion and Exclusion Criteria (see Sections 4.1 and 4.2, respectively).
- Complete APR and PRR trainings prior to patient questionnaires.
- Administer the PD-Q, PHQ-9, GAD-7, PCS, and ISI.
- Record medical history, including OA medical history and AC medical history.
  - For glenohumeral OA patients, OA medical history will include American College of Rheumatology diagnosis details; OA diagnosis date (if available); number of days with index shoulder pain in the last month; previous IA corticosteroid, PRP, or hyaluronic injections; presence of OA in other joints; and prior procedures or surgeries for index shoulder OA.
  - For AC patients, AC diagnosis date (if available); pain duration since onset at Screening; previous IA corticosteroid, PRP, or hyaluronic injections; presence of OA in other joints; and prior procedures or surgeries for index shoulder AC.
- Record patient demographics.
- Record prior treatments and medications.
- Record the average daily shoulder pain with movement score (0 to 10 NRS), SI question, and rescue medication usage in the eDiary.
- Record the pain with duration since onset (AC patients only).
- Perform physical examination.
- Perform shoulder assessment, including active and passive ROM, on the index and contralateral shoulder.

- Perform index shoulder X-ray.
  - X-ray of the index shoulder will include axillary view and true anterior-posterior view.
  - For glenohumeral OA patients, the Screening Visit X-ray will be read centrally to confirm Grade 2 or 3 OA in the index glenohumeral joint based on the Samilson-Prieto classification system.
  - For shoulder AC patients, the Screening Visit X-ray will be read centrally to confirm there is no evidence of OA in the index shoulder.
  - An x-ray acquired within 6 weeks of the Screening Visit may be used for study qualification if the specified imaging protocol was followed. The x-ray will be read centrally to confirm there is no evidence of OA in the index shoulder.
- Obtain vital signs.
- Perform ECG.
- Record height and weight and calculate BMI.
- Collect blood samples for hematology and chemistry, including hemoglobin A1c.
- Perform HIV, HBsAg, and HCV screens.

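### The HbA1c exclusion gives two cut-offs that are not equivalent, so results of about 7.6% to 8.0% pass in one unit and fail in the other

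*Combined protocol and SAP*

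**What the plan says.** Section 4.2, criterion 32, excludes a patient who "Has uncontrolled diabetes as indicated by a hemoglobin A1c of >8% (>59 mmol/mol". The bracket presents the mmol/mol value as the same limit in the other unit, and it carries its own greater-than sign.

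The criterion is a hard rule. The lead-in to Section 4.2 reads: "A patient who meets any of the following criteria will be excluded from participation in the study". Criterion 32 leaves no room for investigator judgment in applying it.

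HbA1c is measured once, at Screening. Section 6.3 lists "Collect blood samples for hematology and chemistry, including hemoglobin A1c", Table 1 in Appendix A marks it at the Screening Visit only, and Appendix B lists it under hematology. None of these gives a reporting unit. The protocol contains no other HbA1c limit, no conversion between the units, and no statement of which unit takes precedence.

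**The concern.** An exclusion limit printed in two units should classify every patient the same way in both. Here the figures look too far apart to be one threshold. If so, a patient whose result falls between them meets the criterion in one unit and not in the other.

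What is at stake is consistent eligibility. Uncontrolled diabetes is a natural safety exclusion in a trial of an injected corticosteroid, although the protocol does not label it as one. Diabetes is also relevant to the adhesive capsulitis cohort, since Section 1.1 notes that "the incidence is higher among patients with diabetes than observed in the general population". If results are reported or programmed in mmol/mol, or in both units, a patient in the gap could be turned away or enrolled depending on the unit consulted. A patient enrolled under the percent figure could later be recorded as an eligibility deviation against the mmol/mol figure.

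**Working it through.** **Inputs from the protocol.** Both limits come from Section 4.2, criterion 32: above 8%, and above 59 mmol/mol.

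**Input assumed.** The standard linear relation between the two HbA1c units, which the protocol does not give:

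- % = 0.09148 × (mmol/mol) + 2.152
- in its inverse form, mmol/mol = 10.93 × % − 23.50

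**Step 1: try to reproduce the 59.**

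- (8 − 2.152) / 0.09148 = 5.848 / 0.09148 = 63.93 mmol/mol
- by the inverse form, 10.93 × 8 − 23.50 = 87.44 − 23.50 = 63.94 mmol/mol

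The printed 59 is not reproduced. The difference is 63.9 − 59 = 4.9, or about 5 mmol/mol.

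**Step 2: convert the 59 to percent.**

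- 0.09148 × 59 + 2.152 = 5.397 + 2.152 = 7.55%

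The difference is 8.00 − 7.55 = 0.45 percentage points.

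**Step 3: see whether rounding explains it.**

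- 8% read as anything from 7.95% to 8.05% gives 63.4 to 64.5 mmol/mol.
- 59 mmol/mol read as anything from 58.5 to 59.5 gives 7.50% to 7.60%.

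The ranges do not overlap in either unit.

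**Step 4: find which results are classified differently.** HbA1c is taken to one decimal in percent, and the mmol/mol value is rounded to an integer before it is compared with 59.

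| HbA1c (%) | mmol/mol | Excluded by >8%? | Excluded by >59 mmol/mol? |
|---|---|---|---|
| 7.5 | 58.5 | no | no |
| 7.6 | 59.6 | no | yes |
| 7.7 | 60.7 | no | yes |
| 7.8 | 61.7 | no | yes |
| 7.9 | 62.8 | no | yes |
| 8.0 | 63.9 | no | yes |
| 8.1 | 65.0 | yes | yes |

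The conflict covers 7.6% to 8.0%, or about 60 to 64 mmol/mol. It runs in one direction only: the mmol/mol figure is the stricter of the two and can only add exclusions. At 7.5% and below neither limit excludes, and at 8.1% and above both do.

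**The case against.** The best case on the other side is that the conflict will seldom bite.

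- **Likely unit in use.** Section 3.1 places all sites, approximately 35, in the United States. Criterion 32 puts percent first, and the protocol gives blood glucose in mg/dL elsewhere (Section 1.3.2). The natural reading is that the percent figure operates and the bracket is a faulty gloss.
- **One laboratory.** Table 1 sends hematology to the central laboratory, and Section 8.8 requires the tests in Appendix B to follow the Central Laboratory Manual. Sites are therefore unlikely to receive results in different units.
- **A backstop.** Criterion 42 lets the investigator exclude a patient on safety grounds whatever the HbA1c figure.
- **No statistical effect.** Eligibility is settled before randomization, so a misread limit applies to both arms alike.
- **Outside constant.** The mismatch shows only once a conversion from outside the protocol is applied.

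Most of this stands as a limit on impact. None of it makes the two figures equal. That percent governs is an inference, because the protocol states neither a reporting unit nor an order of precedence. Criterion 42 does not correct the number. The conversion is a relation between units rather than a study result, and the gap of about 5 mmol/mol is roughly ten times the half-unit that rounding to an integer allows. It remains true that an HbA1c edit check or laboratory flag is not described in the protocol: Section 10.1.5 mentions programmed validation checks only in general terms. The practical consequence is therefore conditional on how results are reported and checked.

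**Conclusion.** The concern holds. Criterion 32 states two different thresholds as if they were one, about 5 mmol/mol or 0.45 percentage points apart. Results from about 7.6% to 8.0% are eligible by one and excluded by the other.

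The finding rests on the standard unit conversion, stated as an assumption; both forms of it agree to within 0.02 mmol/mol at 8%. The number of screened patients in the gap cannot be estimated from the documents and is likely to be small. The likely consequence is at most a few avoidable screen failures or disputed eligibility deviations. The sample size, type I error control and primary analysis are not affected. This is a minor correction, worth making because the figure is an operative eligibility limit. No view is taken on which of the two limits was intended.

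**What to change.** Reconcile the two figures in Section 4.2, criterion 32, so that both units express a single threshold chosen by the sponsor's clinicians. State in the criterion or in Appendix B which unit the central laboratory reports and which governs eligibility. Carry the same value into any laboratory flag and any eligibility check in the data-capture system. If patients have already been screened, list those with results of about 7.6% to 8.0% and record which limit was applied to each.

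The cost is one number in the protocol, carried with the next amendment, and the matching entry in the laboratory and data-capture specifications. No analysis changes.

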### 4.3 Withdrawal Criteria

If a patient withdraws, he/she should continue to be followed for safety assessments up to 24 weeks after treatment. A patient may withdraw from the study at any time for any reason, without any consequences. In addition, a patient may be withdrawn from the study for the following reasons:

- Adverse event (typically a serious adverse event [SAE])
- Patient choice (withdrawal of consent, Investigator will attempt to ascertain reason)
- Protocol violation/noncompliance
- Lack of efficacy (lack of expected or desired effect related to a therapy)
- Physician decision (a position, opinion, or judgment reached after consideration by a physician with reference to the patient)
- Progressive disease (a disease process that is increasing in extent or severity)
- Study terminated by Sponsor
- Technical problem (a problem with some technical aspect of a clinical study, usually related to an injection)
- Other

If a patient withdraws from the study, he/she may request destruction of any samples taken and not tested, and the Investigator must document this in the study site records.

If a patient withdraws prematurely from the study due to the above criteria or any other reason, study staff should make every effort to complete the full panel of assessments scheduled for the EOS Visit (Week 24) (see Section 6.6). The reason for patient withdrawal must be documented in the electronic case report form (eCRF). Those patients who withdraw from the study will be referred to a physician for follow-up care.

Withdrawn patients will not be replaced.

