#### 3.1 Summary of Study Design

This is a Phase 2, multicenter, randomized, double-blind, placebo-controlled, parallel-group study designed to evaluate the efficacy and safety of a single IA injection of either 5 mL of the reconstituted FX006 (32 mg) or 5 mL of placebo (sterile normal saline) in separate cohorts of patients with a documented history of glenohumeral OA or shoulder AC.

This study will be conducted at approximately 35 study sites in the United States. Patients will be screened to confirm the diagnosis of OA or AC and eligibility based on the Inclusion and Exclusion Criteria. Eligible patients will be randomized to treatment on Day 1. Glenohumeral OA patients will be stratified by the Baseline average daily shoulder pain with movement score (0 to 10 numeric rating scale [NRS]) (5.0 to <7.0 or ≥7.0 to 9.0). Shoulder AC patients will be stratified by the Baseline average daily shoulder pain with movement score (0 to 10 NRS) (5.0 to <7.0 or ≥7.0 to 9.0), and pain duration since onset at Screening (1 to 3 months, inclusive, or >3 to ≤6 months).

Approximately 250 male or female patients, 35 to 80 years of age, inclusive (approximately 136 glenohumeral OA patients and approximately 114 shoulder AC patients), will be enrolled in this study. The study duration is approximately 27 weeks, including a Screening Period of up to a maximum of 3 weeks and treatment on Day 1 followed by a 24-week Treatment Evaluation Period. The study design can be seen in Figure 1.

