### **5.6.1 Excluded Medications and/or Procedures**

The following medications are excluded for the duration of the study. If a patient is taking any of these excluded medications, they must, after signing the ICF, complete a washout consisting of a period of 5 half-lives of the excluded drug 7 days prior to Day 1.

- Oral nonsteroidal anti-inflammatory drugs (NSAIDs).
- Aspirin (>325 mg/day).
- Centrally-acting pain medications (e.g., pregabalin, gabapentin, duloxetine, and/or milnacipran) unless specifically allowed, or allowed with restriction, in the protocol.
- Opioids.
- Topical therapies (e.g., NSAIDs, capsaicin, lidocaine patches, CBD products, or other local treatments) applied to the index shoulder.
- Anesthetic medications injected locally in the index shoulder (other than the selected anesthetic if used for the IA injection procedure).
- Muscle relaxants (e.g., cyclobenzaprine, tetrazepam, and/or diazepam).

The following medications and/or procedures should not be taken and/or performed throughout the study:

- IV or IM corticosteroids within 3 months of the Screening Visit.
- Oral corticosteroids within 1 month of the Screening Visit.
- Inhaled, intranasal, or topical corticosteroids within 2 weeks of the Screening Visit.
- IA corticosteroids in any joint within 3 months of the Screening Visit.
- IA viscosupplementation (hyaluronic acid) or any IA intervention (e.g., IA injection) in the index shoulder within 6 months of the Screening Visit.

- Any investigational drug, biologic, or device within 3 months of the Screening Visit.
- Chemotherapeutic agents, immunomodulators, or immunosuppressants other than corticosteroids within 5 years of the Screening Visit.
- Live or live-attenuated vaccines within 3 months of the Screening Visit.
- Significant changes with regard to physical activity and lifestyle, within 1 month prior to the Screening Visit and changes throughout the duration of the study.

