#### 6.6 Early Termination Visit and Withdrawal Procedures

The end of treatment for patients completing the study is the EOS Visit (Week 24). For patients who withdraw from the study prior to completion (Early Termination [ET]), all EOS Visit procedures will be performed at the corresponding visit. See Section 6.5.2 for the procedures that will be performed.

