#### 9.4.1.2 Secondary efficacy analyses

The key secondary change from Baseline endpoints will be analyzed with longitudinal mixed models for repeated measures with fixed effects for treatment group, study week, treatment-by-week interaction, analysis site, and Baseline score. Patient will be the random effect. Treatment differences from control will be estimated via LSMs from the analysis model along with 95% CIs and associated 2-sided p-values. This model assumes data are missing at random and includes only observed data. In addition, the model for shoulder AC will also include a covariate for pain duration since onset.

Multiplicity will be addressed by analyzing the key secondary endpoints sequentially in the order presented in the protocol, testing each endpoint at the nominal  $\alpha = 0.05$ , 2-sided level to ensure overall type I error control at the 2-sided 0.05 level.

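### Patients may be withdrawn for lack of efficacy after a one-time injection, and Section 4.3 names only safety follow-up afterwards, so pain data for the Week 8 and Week 12 endpoints can be lost

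*Combined protocol and SAP*

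**What the plan says.** Section 3.1 describes "a single IA injection of either 5 mL of the reconstituted FX006 (32 mg) or 5 mL of placebo (sterile normal saline" as the whole of study treatment. There is no later dose to stop.

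Section 4.3 says a patient may be withdrawn from the study for listed reasons. These include "Lack of efficacy (lack of expected or desired effect related to a therapy", "Progressive disease (a disease process that is increasing in extent or severity" and "Protocol violation/noncompliance". On what follows, it says the patient "should continue to be followed for safety assessments up to 24 weeks after treatment". It also asks staff to make every effort to complete the full Week 24 panel when a patient leaves early. Section 6.6 repeats this: "all EOS Visit procedures will be performed at the corresponding visit". Section 6.5.2 shows that the panel contains SPADI, ASES, EQ-5D-5L, PGIC, range of motion and a review of the diary. Withdrawn patients are not replaced.

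The primary endpoint (Section 7.1.1) is an AUC over 8 weeks of weekly mean pain, built from daily diary entries (Section 7.2.1). All five secondary endpoints (Section 7.1.2) are at Week 12. Of the secondary mixed model, Section 9.4.1.2 says "This model assumes data are missing at random and includes only observed data". Section 9.4.1.1 leaves details of the AUC analysis to the SAP. Section 9.1 makes sensitivity analyses for missing data optional. Section 9.4.6 states no dropout rate.

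**The concern.** In a trial with continuing treatment, stopping treatment and leaving the study are separate events, and a good protocol keeps them apart. Here there is nothing to stop after Day 1, so withdrawal acts only on data collection. Two of the listed reasons, lack of efficacy and progressive disease, are close to the outcome being measured. A patient who does badly can therefore leave the data because of doing badly.

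There is a plausible pressure in that direction. Section 5.6.1 opens with "The following medications are excluded for the duration of the study" and goes on to list oral NSAIDs, opioids and topical treatments. Inclusion criterion 8 in Section 4.1 separately rules out physical therapy, acupuncture, TENS and bracing. Acetaminophen rescue is supplied throughout (Section 5.5.6), but a patient who wants more than that must leave or depart from the protocol.

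The stake is data that no analysis can recreate. A model can predict the scores after withdrawal, but only later scores can show whether the prediction was right.

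**Working it through.** **1. What a withdrawn patient still supplies.**

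| Needed | Source | After withdrawal at, say, Week 4 |
|---|---|---|
| Weekly mean pain over 8 weeks (primary) | Daily diary | 4 of 8 weeks present; no provision for the other 4 |
| Weekly mean pain at Week 12 | Daily diary | No provision |
| SPADI pain, SPADI disability, PGIC, external rotation at Week 12 | Site visit | One early panel at Week 4; no provision at Week 12 |
| Safety to Week 24 | Follow-up under Section 4.3 | Continues |

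The early panel is a real efficacy measurement, but it is taken once and at the wrong week.

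**2. The plan's own power.** Inputs from Section 9.4.6: two-sided alpha 0.05, 1:1 allocation; OA difference 1, SD 2, N = 136 (68 per arm); AC difference 1.2, SD 2.1, N = 114 (57 per arm). With the normal approximation, power = Φ(d / (SD × √(2/n)) − 1.96).

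- OA: 1 / (2 × √(2/68)) − 1.96 = 0.956, power 83.0%.
- AC: 1.2 / (2.1 × √(2/57)) − 1.96 = 1.091, power 86.2%.

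Both agree with the stated figure of more than 80%.

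**3. Lost numbers alone.** The loss rates are assumed, because the documents give none. Multiply n by (1 − loss) and treat a lost patient as contributing nothing.

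| Assumed loss | OA power | AC power |
|---|---|---|
| 5% | 81.1% | 84.5% |
| 10% | 79.0% | 82.5% |
| 15% | 76.7% | 80.3% |
| 20% | 74.1% | 77.9% |

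OA falls below 80% at 10% loss. This is somewhat pessimistic, since the mixed model uses the early scores of patients who leave.

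**4. Possible bias.** Let p be the share missing at the time point and g the mean amount by which true unseen pain exceeds the model's prediction. The bias in the treatment difference is p(placebo) × g(placebo) − p(FX006) × g(FX006). If g is the same in both arms, this is the difference in shares times g. Assume 15% loss on placebo and 5% on FX006, an excess of 10 percentage points, and g from 0.5 to 2 NRS points.

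| g | Bias (points) | Share of OA difference of 1 | Share of AC difference of 1.2 | OA power | AC power |
|---|---|---|---|---|---|
| 0.5 | 0.10 × 0.5 = 0.05 | 5% | 4% | 74.8% | 79.2% |
| 1 | 0.10 × 1 = 0.10 | 10% | 8% | 70.2% | 75.6% |
| 2 | 0.10 × 2 = 0.20 | 20% | 17% | 60.0% | 67.4% |

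The power columns use the formula of step 2, with the difference reduced by the bias and n reduced by the 10% average loss. The OA row for g = 1, for example, is 0.90 / (2 × √(2/61.2)) − 1.96 = 0.529, or 70.2%.

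These figures apply to a single time point such as Week 12. For the 8-week AUC expressed as a weekly average, the effect shrinks with the fraction of weeks missing (a half for the Week 4 example). If the excess loss were on FX006, or if unseen scores were better than predicted, the sign would reverse.

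**The case against.** The case against is partly right, and it limits how far the point can go.

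- **Safety follow-up only.** A reader might infer that no efficacy data are collected once a patient withdraws. Sections 4.3, 6.5.2 and 6.6 do not support that: a full panel with efficacy items is sought at withdrawal. Nor do the documents forbid later diary entries; they are silent on them. What stands is that silence leaves about 35 sites with no instruction to continue.
- **Noncompliance.** It is tempting to call all three reasons outcome-driven. Noncompliance need not be. Withdrawal is also permissive in Section 4.3, the Full Analysis Set in Section 9.3 has no exclusion for deviations, and Section 4.3.1 requires sites to pursue patients who miss visits.
- **The missing-at-random model.** A reader might conclude that the secondary model is invalid because leaving depends on pain. That does not follow. A patient who leaves for lack of efficacy will usually have recorded high scores first, and dependence on recorded scores is compatible with the assumption. It fails only if leaving depends on unseen scores beyond that history. What remains is that the assumption cannot be checked.
- **Different loss by arm.** Section 1.3.3 reports less rescue use with FX006 in knee OA. It is tempting to read this as evidence of more placebo withdrawals here. It says nothing about withdrawal and nothing about adhesive capsulitis.
- **Size.** Both bias inputs are assumed. A gap of 2 points equals the whole OA standard deviation, so the top of the range is severe.

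**Conclusion.** The point holds in a limited form. The protocol allows outcome-related withdrawal after a one-time injection and makes no provision for efficacy data after the withdrawal visit. Following it as written can lose part of the primary AUC and all Week 12 data for such patients. The loss is avoidable and cannot be reversed later.

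Whether the results would be biased, by how much and in which direction, cannot be settled from the documents. The range of 0.05 to 0.20 points rests on an assumed 10-point excess of placebo withdrawals and an assumed gap of 0.5 to 2 points, equal in both arms. A reader might infer a bias in favour of FX006. The documents do not support that either: if placebo leavers do worse than predicted, the effect is understated and the cost is power, not a false positive.

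The text available contains no rule for missing weeks in the AUC, so the primary analysis could not be judged on this point. No such rule would restore uncollected scores. This should be changed, but it does not undermine the design.

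**What to change.** Leave the list of withdrawal reasons as it is. In Sections 4.3 and 6.6:

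1. Distinguish withdrawal of consent from every other reason.
2. Extend the follow-up sentence in Section 4.3 so that it covers efficacy as well as safety assessments.
3. State that, unless consent is withdrawn or the patient is lost to follow-up, the daily pain diary and the scheduled SPADI, PGIC and range-of-motion assessments continue at least through Week 12.
4. Record any new therapy with its start date.

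The SAP should then say how scores recorded after another therapy are used in the primary and secondary analyses.

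The cost is amendment wording and a line in the consent form. The diary and instruments are already in use. There are two small downsides. Some scores will follow other therapies and need the stated rule. Some withdrawn patients will also have efficacy assessments added to their safety follow-up, for which Section 4.3 gives no visit schedule. The change concerns data collection only and leaves patient care to the investigator.
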